#### **Data Analysis**

*Aim 1: To develop the Siblings FORWARD program.* Directive content analysis will be used to interpret the data and transcripts from the focus groups and individual interviews. Directive content analysis will result in refined objectives, content, and format of the Siblings FORWARD program that will be implemented and assessed in the subsequent open trial and RCT. In a series of recursive analyses, the first level of analysis will involve open coding, a strategy which involves investigators identifying all responses to focus group questions. To ensure reliability of interpretations, analyses of transcripts require multiple readings and coding by multiple investigators. The analytic team (Drs. [name] and [name]) will each independently openly code one focus group transcript. We will then jointly compare and contrast the individual coding to identify recurring patterns in the responses to each question to develop initial operational definitions that describe the conceptual categories for each question. Specifically, we will identify conceptual categories related to family/sibling involvement in future planning, unmet needs of adults with ASD, and perceptions of the Siblings FORWARD program being developed. Coding will be done in NVivo to facilitate sorting and comparison of the data.

The second level of analysis, axial coding, will focus on sorting and classifying the constructs to explicate the perspectives of the siblings, service providers, and adults with ASD. Using the agreed upon coding definitions, each investigator will independently code the remaining transcripts from the focus groups and interviews. The team will discuss relevant codes and establish axial coding categories in which subcategories from the open coding are then regrouped into more conceptual categories that refer to types of existing and future supports and services and barriers to implementation to promote increased sibling engagement and positive outcomes for the adult with ASD. Once a new set of subcategories has been identified, the research team will independently examine all transcripts to further develop the objectives, content, and format of the Siblings FORWARD program. We will conduct ongoing validity checks regarding analytic categories, revising the coding scheme as needed. NVivo will be used to organize the data according to the axial coding scheme. We will compare and contrast the data across all focus groups and in-depth interviews.

We will ensure that our analyses are credible using several procedures. For both open and axial coding, each coder will compare their findings to assess coder interpretations. Through discussion and comparison of the coder's reasoning, coder discrepancies will be resolved and coding definitions and constructs will be modified. To address the theoretical validity of our interpretations, we will discuss initial open codes and survey questions with the CAB.

*Aim 2: To assess feasibility and acceptability of the Siblings FORWARD program.* Qualitative feasibility and acceptability data will be collected during the open trial and RCT portions of the proposed project.

Acceptability (open trial and RCT): Qualitative data about perceptions of program usefulness and value collected during exit interviews with providers and participants will be evaluated using the qualitative methods outlined for Aim 1. Participant understanding of measures and procedures (open trial): Missing data and inconsistent response patterns on measures completed by siblings will be recorded. Data collection time will be calculated descriptively (mean, standard deviation, and range); participant burden associated with completing study measures will be captured qualitatively and summarized using content analysis. Enrollment and retention (RCT): Enrollment will be evaluated by calculating the number of eligible participants who chose to enroll in the trial. Descriptive statistics show the average number of sessions completed by participants and retention and follow-up rates. To assess selective attrition, we will evaluate the demographic and clinical characteristics of participants who completed the program versus those who did not using t-tests and chi squares. Adherence (RCT): Providers' fidelity to the manual will be assessed by evaluating video recordings of sessions against checklists of required components and calculating the percentage of required components that were present in each session; 20% of sessions will be coded for fidelity. Appropriateness of outcome measures (RCT): Psychometric properties of measures (alpha coefficients, means, SDs) and descriptive statistics of change scores from pre- to post-program time points (including confidence intervals) will be calculated.

*Aim 3: To assess the outcomes of participation in the Siblings FORWARD program.* We will examine whether the program shows promise of being successful with the intended population by conducting two-way repeated measures ANOVAs examining main effects of intervention condition (Siblings FORWARD vs. control) and repeated for assessment (pre- post- and 3-month follow up) on measures for program targets (sibling problem solving skills, family communication, future planning self-efficacy, barriers to future planning, and knowledge of services and family future plans) and proximal outcomes (sibling plan of action and adult with ASD quality of life, perceptions of unmet needs, and family relationships). Post-hoc tests will be used in multiple comparisons between groups and within each group. Effect sizes (Cohen's d) will be calculated using the mean difference of the changes recorded from pre- to post-program. We will also analyze percent change and reliable change. If data are missing, analyses will be performed using the 'last observation carried forward' method for intention-to-treat analysis. We will examine descriptive statistics (mean, SD, confidence intervals) at the participant level for patterns and direction of change on outcome measures. We will conduct intent-to-treat analyses if there is program attrition. Finally, we will examine benefit of the program to control participants who elect to participate in the Siblings FORWARD program using one-way ANOVAs (pre to post-program) on treatment targets and proximal outcomes.

We will conduct a preliminary investigation of potential moderators of program effectiveness, including characteristics of the sibling (BAP), family (income, race/ethnicity, English as the primary language, number of family members with ASD), and adult with ASD (severity of ASD symptoms, problem behaviors, functional independence). We will calculate correlations between these variables and change scores in primary outcome variables, and independent samples t-tests between these variables and program completion status.

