RCT. The final phase of the proposed project will implement an RCT to examine whether the program is feasible and associated with improvements in the treatment targets (see Measures and Figure 1). Thirty-six siblings will be recruited and randomly assigned to participate in Siblings FORWARD (N=18) or receive written materials about future planning (N=18). Siblings assigned to Siblings FORWARD will complete Time 1 (pre-program) measures, participate in the 6-session intervention over 4 months, complete Time 2 measures immediately after program completion, and complete Time 3 measures 3 months later. Those assigned to the control condition will complete Time 1 measures at the time of enrollment, Time 2 measures 4 months after enrollment, and Time 3 measures 7 months after enrollment. With the exception of the clinician rating of the sibling's ASD symptoms (see Measures), all data will be collected by the Boston University study team via home visits in order to separate data collection from the Arc providers. Adults with ADS and their families will determine whether the adult with ASD can complete the questionnaires (see Methods). When possible, the adult with ASD will complete the measures independently in the presence of a Boston University research team member. These measures can also be completed with the support of a research team member, sibling, parent, or service provider. Given possible geographic separation, sibling data will be collected via mailed questionnaire packets. We will track this data collection method to inform future data collection logistics.

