#### Program Targets: Sibling Future Planning Knowledge & Skills (Measured at Time 1, Time 2, & Time 3)

1. Problem Solving Skills. Siblings will complete the Social Problem-Solving Skills Inventory-Revised (SPSI-R). This 52-item self-report measure was used in a problem-solving intervention with mothers of children with ASD. Five dimensions assess how the individual strategically approaches a situation (positive problem orientation, negative problem orientation, rational problem solving, impulsivity carelessness style, and avoidance style). Siblings will rate the extent to which each item is 1 (not at all true) to 5 (extremely true) of them. Higher scores indicate better problem-solving skills. Good reliability is reported.
2. Family Communication about Future Planning. Siblings will rate the frequency with which they have had family discussions about planning for the future of their brother/sister with ASD. Siblings will respond to a 1-item measure previously used in a study evaluating a peer-support program for aging caregivers of adults with intellectual and developmental disabilities. The item is scored on a 3-point scale (not discussed at all, discussed somewhat, discussed a great deal).
3. Future Planning Self-Efficacy. We will adapt the Caregiving Self-Efficacy Scale that has been used by with parents and adult siblings to evaluate participation in a peer-support intervention for aging caregivers. The scale consists of 6 items rated on a 4-point scale (strongly disagree to strong agree). Sample items include: I honestly believe I can be a good caregiver to my relative; If anyone can find the answer to what is troubling my relative, I can. The scale has good reported reliability (alphas .73-.82).
4. Sibling Barriers to Future Planning. Siblings will complete a list of barriers to future planning adapted from a measure used by Heller and Caldwell. The original list included 12 barriers such as: difficulty finding helpful contact persons within the service system, emotional barriers involved with thinking their parents' mortality, or disagreement with a relative with a disability about the future.
5. Knowledge of adult services and delivery systems. Siblings will rate their knowledge of the services received or needed by their brother/sister with ASD. We will use a list of 12 adult services: physical

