#### Proximal Outcomes: Sibling Behavior & Adults with ASD (Timing indicated below)

1. **Sibling Plan of Action (T2)**. Siblings will submit a written plan of action at the final session; control participants will complete this plan at Time 2. We will use a template on which siblings will detail their short- and long-term goals with respect to family future planning and concrete next steps. Researchers will rate each plan according to the following criteria: (1) inclusion of short- and long-term goals and next steps, (2) appropriate scope of next steps, (3) alignment with the needs and/or preferences of the adult with ASD, (4) accuracy (e.g., are they identifying the right resources to meet the identified goal?), and (5) sufficient detail (e.g., including the names and phone numbers of actual resources vs. making vague plans). At the 3-month follow up time point, we will assess whether or not the sibling attempted or achieved their primary short-term goal, the steps they took to achieve their goal, and concrete outcomes of the sibling's engagement in family future planning (e.g., family made an appointment with a special needs lawyer).
2. **Adult with ASD: Quality of Life (T1 & T3). Proxy report**: Siblings will rate their brother/sister's quality of life using the Life Experiences Checklist. This has been used as a proxy-report measure by family members and support staff to rate the QOL of adult with ASD. Five sections cover the individual's home environment, leisure activities, relationships, freedom, and opportunities. **Self-report**: Adults with ASD will complete the WHOQOL-BREF, a shorter version of World Health Organization Quality of Life assessment, the WHOQOL-100, which includes 26 items rated on a 5-point scale addressing physical and psychological health, social relationships, and environment. This measure has been used with adults with ASD, including [name] collaborative study with [name]. We will modify administration as described by Hong and colleagues to ensure greater accessibility across the autism spectrum.

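### Aim 3's only between-arm test with a specified contrast averages in the pre-program visit, so it targets 2d/3 (program targets) or d/2 (quality of life) of a sustained effect d

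*Combined protocol and SAP*

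**What the plan says.** The Aim 3 paragraph of Data Analysis states how success will be judged: "We will examine whether the program shows promise of being successful with the intended population by conducting two-way repeated measures ANOVAs". The models are specified as "two-way repeated measures ANOVAs examining main effects of intervention condition (Siblings FORWARD vs. control) and repeated for assessment (pre- post- and 3-month follow up"). The effect named for the arm comparison is the main effect of condition, with the pre-program, post-program and 3-month assessments as the repeated factor. The same model is listed for every program target and every proximal outcome. No condition-by-time term and no baseline-adjusted comparison is named.

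Three other planned quantities bear on the point:

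- Aim 3, post-hoc tests: "Post-hoc tests will be used in multiple comparisons between groups and within each group". No visit or contrast is given.
- Aim 3, effect size: "Effect sizes (Cohen's d) will be calculated using the mean difference of the changes recorded from pre- to post-program". The text does not say that this is a difference between arms, and it gives no counterpart for the 3-month visit.
- Aim 2, appropriateness of outcome measures: "descriptive statistics of change scores from pre- to post-program time points (including confidence intervals) will be calculated". This is descriptive and serves a different aim.

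The visit schedule is in Procedures (RCT) and Measures. Time 1 comes before the program: "Siblings assigned to Siblings FORWARD will complete Time 1 (pre-program) measures". The targets have three visits: "Program Targets: Sibling Future Planning Knowledge & Skills (Measured at Time 1, Time 2, & Time 3"). Quality of life has two: "Adult with ASD: Quality of Life (T1 & T3"). The sibling plan of action is rated at T2 only, with goal attainment followed up three months later.

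**The concern.** The main effect of condition in a repeated measures ANOVA is the arm difference in the average over all visits. Under randomisation the expected arm difference at Time 1 is zero. Including that visit pulls the contrast towards zero by a fixed fraction and brings in whatever imbalance chance produced at Time 1. With 18 siblings per arm that imbalance can be sizeable.

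What is at stake is the signal taken into the larger trial, for which Table 4 schedules a grant application in the same quarter as the RCT analyses. The named test may be non-significant beside a sizeable pre-to-post effect size, and the plan gives no rule for reading the two together. Separately, a repeated factor cannot be fitted to a plan of action that is rated once.

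**Working it through.** **Inputs from the documents.** 36 siblings, 18 per arm (Procedures, RCT). Visits: T1, T2, T3 for program targets; T1 and T3 for quality of life; T2 for the plan of action (Measures). Time 1 is pre-program.

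**Not in the documents.** Alpha, power, effect size, SD and within-person correlation are not stated, so there is no planned figure to reproduce. Assumed below: two-sided 5%, SD 1 at each visit, compound symmetry with correlation r, no missing data, and an effect d sustained at T2 and T3.

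**Step 1: size of the contrast.** This needs only the visit schedule, equal expected T1 means and a sustained effect.

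- Program targets: (0 + d + d)/3 = 2d/3, one third lost.
- Quality of life: (0 + d)/2 = d/2, one half lost.

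Simulation at d = 0.8 and r = 0.5 gave mean estimates of 0.535 (expected 0.533) and 0.402 (expected 0.400). The between-arm difference in pre-to-post change gave 0.798, so the numerator of the planned Cohen's d, read as a difference between arms, is not attenuated.

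**Step 2: power for the three-visit targets.** Let k = 2/18 = 0.111.

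- Main effect: estimate 2d/3, SE = sqrt[k(1+2r)/3], 34 df.
- Change contrast (mean of T2 and T3 minus T1): estimate d, SE = sqrt[1.5k(1−r)], 34 df.
- T1-adjusted mean of T2 and T3: estimate d, SE = sqrt[k((1+r)/2 − r²)], 33 df.

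Worked case, d = 0.8 and r = 0.6. Main effect: 0.533 / sqrt(0.111 × 0.733) = 0.533/0.285 = 1.87. T1-adjusted: 0.8 / sqrt(0.111 × 0.44) = 0.8/0.221 = 3.62. These are the noncentralities. The noncentral t distribution gives:

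| d | r | Main effect | Change contrast | T1-adjusted |
|---|---|---|---|---|
| 0.8 | 0.1 | 69% | 52% | 89% |
| 0.8 | 0.25 | 59% | 59% | 87% |
| 0.8 | 0.3 | 57% | 62% | 88% |
| 0.8 | 0.6 | 44% | 85% | 94% |
| 0.8 | 0.8 | 39% | 99% | over 99% |
| 0.5 | 0.1 | 34% | 24% | 51% |
| 0.5 | 0.6 | 21% | 47% | 59% |

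Main effect and change contrast tie where (4/3)/(1+2r) = (2/3)/(1−r), that is r = 0.25. Below that the change contrast has less power. The squared noncentrality of the T1-adjusted test divided by that of the main effect is 1.5/(1−r), at least 1.5 for any r from zero upwards. In simulation the adjusted test's power was up to about one point below the closed form, because it pays for the observed T1 imbalance.

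**Step 3: chance imbalance.** The T1 arm difference has SD sqrt(k) = 0.33. One such SD moves the main-effect estimate by 0.33 × (1+2r)/3, which is 0.13 SD at r = 0.1, 0.24 at r = 0.6 and 0.29 at r = 0.8. The T1-adjusted estimate is essentially uncorrelated with the T1 difference.

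**Step 4: disagreement between test and effect size** (simulation, d = 0.8). This counts trials with a between-arm pre-to-post change of at least 0.5 SD, an illustrative cut-off, and a non-significant test. For the main effect: about 23%, 34%, 46% and 56% at r = 0.1, 0.3, 0.6 and 0.8. For the T1-adjusted test: about 5%, 5%, 2% and 0.1%.

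**Step 5: Type I error.** At d = 0 the simulated rate was 4.9–5.2% for the main effect and 4.8–5.3% for the adjusted test.

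**The case against.** The best defence is that the text is proposal shorthand for an analysis of change. A two-way ANOVA normally outputs the condition-by-time term. Cohen's d, percent change, reliable change and the moderator correlations all use change. A post-hoc between-group test at T2 or T3 would target the full d, with about 64–65% power at d = 0.8 whatever r is. This shows what was probably meant. It does not settle what will be tested: no interaction or adjusted term is named, and the post-hoc tests have no visit. Choosing among these after seeing output is what a plan should prevent.

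Two further points stand. The loss of one third is on the raw scale. Standardised by the SD of the three-visit mean, the main effect is (2/3)/sqrt[(1+2r)/3] times d: 1.05 at r = 0.1, 0.91 at r = 0.3 and 0.78 at r = 0.6. And naming the interaction is not always better: at d = 0.8 its 2-df test has 52% power at r = 0.3 against 57% for the main effect, though 78% against 44% at r = 0.6. At r = 0.1 the change contrast also disagrees with the effect size in about 24% of trials, so at low r much of the disagreement reflects the small sample. These points argue for T1 adjustment over a bare interaction or change test. They do not defend the main effect.

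Finally, this is a pilot with no stated alpha, power or success threshold, and Design Considerations & Future Directions leaves efficacy to larger trials. That limits the harm.

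**Conclusion.** The point holds for the main-effect contrast and should be fixed. That contrast is the only between-arm one the plan specifies. It targets 2d/3 for program targets and d/2 for quality of life, on the raw scale, if the effect is sustained. These factors need no assumed SD, correlation or effect size. The power and disagreement figures do rest on the assumptions listed in the working.

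A reader might infer more than the documents support:

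- *That no undiluted between-arm comparison is planned.* Post-hoc between-group tests are planned; they are unspecified, not absent.
- *That every effect estimate will be attenuated.* The planned Cohen's d is on pre-to-post change and is not.
- *That the main effect always loses power.* Against a simple change contrast it does not when r is below about 0.25.
- *That a false claim of benefit is likelier.* Type I error is unaffected.

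The consequence is a weaker and noisier test, at odds with the plan's own effect size, feeding the design of the next trial.

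No power is claimed for quality of life. The Program Description treats it as a longer-term improvement, and self-report comes only from adults able to give it, so 18 per arm is an upper limit there. No factor is claimed for unmet needs or family relationships, whose visits Measures does not state.

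**What to change.** - **Program targets:** replace the main-effect test with a between-arm comparison of T2 and T3 scores adjusted for the T1 score, using a model with condition, visit, condition-by-visit and T1 score. Report the adjusted difference with its 95% CI as the program effect. The T2 and T3 differences from this model can replace the unspecified between-group post-hoc tests.
- **Quality of life:** compare T3 between arms, adjusted for T1.
- **Plan of action:** compare the T2 rating between arms, with no repeated factor.
- **Cohen's d:** state that it is the between-arm difference.

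A named condition-by-time (change) contrast is an acceptable fallback, but T1 adjustment is preferred because of the power loss at low correlation.

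The cost is wording and one degree of freedom per model for the T1 covariate. T1 scores for the program targets and quality of life are already collected.

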**Control Condition.** Currently, the standard of care is minimal sibling involvement in future planning or therapeutic activities for their brother/sister with ASD. Some organizations have created resources targeted toward parents (e.g., the Arc's Build Your Plan™ tool), but our preliminary data show that these resources are often perceived by siblings to be minimally helpful and/or overwhelming, which serves to increase their anxiety and decrease the likelihood that they will take action. Several organizations have recently published "tip sheets" for siblings who wish to have a larger role in future planning. The extent to which these tip sheets are accessed by siblings or helpful as standalone resources is unknown, but they are frequently the only resource available to siblings. Given that tip sheets are inexpensive and easy to create and disseminate, it will be important for the proposed project to demonstrate that the outcomes of the Siblings FORWARD program warrant the extra time and resources. Therefore, the control condition will involve providing the same tip sheets and packet of information about resources for adults with ASD as those distributed in Session 3 of the Siblings FORWARD program. After all outcome data are collected from the program and control groups, siblings in the control condition will be offered the opportunity to participate in the Siblings FORWARD program.

**Telehealth Technology. Rationale:** The Siblings FORWARD program will be delivered via synchronous videoteleconferencing (VTC) technology. VTC technology enables the secure delivery of interactive meetings that incorporate audio and video streams of data across multiple sites. The considerable growth of VTC interventions over the last few years has been bolstered by technological advances in VTC, portability of the technology, decreased costs, and increased internet access and technological literacy of the general population. This approach has been employed to overcome geographical barriers to care, which has led to increased availability, accessibility, and acceptability of mental health care delivered remotely. Although most telehealth research focuses on individuals, recent work supports the feasibility of family-based telehealth.

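### Aim 3 does not say which contrast decides whether the program shows promise, and it includes tests that do not compare the two arms

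*Combined protocol and SAP*

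**What the plan says.** The Aim 3 paragraph of Data Analysis opens: "We will examine whether the program shows promise of being successful with the intended population by conducting two-way repeated measures ANOVAs". It names the effects as "examining main effects of intervention condition (Siblings FORWARD vs. control) and repeated for assessment (pre- post- and 3-month follow up". The part at issue here is the assessment factor: "and repeated for assessment (pre- post- and 3-month follow up) on measures for program targets". It continues: "Post-hoc tests will be used in multiple comparisons between groups and within each group". It then gives an effect size: "Effect sizes (Cohen's d) will be calculated using the mean difference of the changes recorded from pre- to post-program".

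The condition by assessment interaction is not mentioned. The paragraph sets no alpha, names no primary outcome, and does not say which of these results would count as promise.

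Three other places bear on the point:
- **RCT design (Procedures):** siblings are "randomly assigned to participate in Siblings FORWARD (N=18) or receive written materials about future planning (N=18".
- **Control Condition (program description):** "the control condition will involve providing the same tip sheets and packet of information about resources for adults with ASD" as are handed out in Session 3. The same paragraph says the trial should show that the program's results justify its added time and resources over such inexpensive materials.
- **Measures:** the targets come under the heading "Program Targets: Sibling Future Planning Knowledge & Skills (Measured at Time 1, Time 2, & Time 3"), and no arm is exempted from them.

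**The concern.** The trial randomizes so that Siblings FORWARD can be compared with written materials alone. Two kinds of result listed in Aim 3 do not make that comparison. A main effect of assessment averages over the arms and asks whether scores moved over time. A within-group post-hoc test asks whether one arm moved from its own baseline. Either can be significant when the program adds nothing.

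Movement in both arms is foreseeable. Controls get the Session 3 materials, both arms answer the same questions on family discussion, services and family plans up to three times, and controls also fill in the plan-of-action template at Time 2.

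The risk of reading such change as benefit is not remote. The same Aim 3 paragraph plans pre-post one-way ANOVAs, with no comparator, for controls who later take up the program, and describes this as examining the program's benefit to them. Table 4 schedules an application for a larger trial in the final quarter, when the RCT is analyzed. If promise were argued from an assessment effect, or from a result significant in the program arm but not in the control arm, that application would rest on evidence that does not separate the program from the tip sheets.

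This is not a multiplicity problem. It would remain with a single outcome and a perfect adjustment.

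**Working it through.** The documents give no power, alpha, SD or expected effect for the RCT, so there is no stated figure to reproduce.

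**Inputs from the documents:** 18 siblings per arm (Procedures, RCT); three assessments for program targets (Measures); a two-way repeated measures ANOVA (Data Analysis, Aim 3).

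**Assumptions not in the documents:** two-sided alpha 0.05; normal data with SD 1; equal correlation ρ of 0.5 or 0.7 between any two occasions; no program effect; both arms gain s SD at Time 2 and keep it at Time 3, so the means are (0, s, s) in each arm.

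**Step 1. Assessment main effect.** The deviations of (0, s, s) from their mean are −2s/3, s/3 and s/3. Their squares sum to 2s²/3. With 36 siblings and within-person error variance 1 − ρ, the noncentrality is

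λ = 36 × (2s²/3) / (1 − ρ) = 24s² / (1 − ρ), on 2 and 68 degrees of freedom.

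- s = 0.3, ρ = 0.5: λ = 24 × 0.09 / 0.5 = 4.32, rejection rate 43%.
- s = 0.3, ρ = 0.7: λ = 24 × 0.09 / 0.3 = 7.2, rejection rate 65%.
- s = 0.5, ρ = 0.5: λ = 24 × 0.25 / 0.5 = 12, rejection rate 87%.
- s = 0.5, ρ = 0.7: λ = 24 × 0.25 / 0.3 = 20, rejection rate 98%.

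**Step 2. Condition by assessment interaction.** Its noncentrality depends only on how the difference between arm means varies over occasions. When the arms change equally that difference is zero throughout, so λ = 0 and the rejection rate is 5% whatever s is.

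**Step 3. Within-arm pre-post test, program arm.** This is a paired t-test with n = 18 and noncentrality s√18 / √(2(1 − ρ)).

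- s = 0.3: 0.3 × 4.243 / 1 = 1.27 at ρ = 0.5, power 22%; 0.3 × 4.243 / 0.775 = 1.64 at ρ = 0.7, power 34%.
- s = 0.5: 2.12 and 2.74, power 52% and 73%.

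**Step 4. Simulation of the same design**, 20,000 trials per scenario, no program effect:

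| Shared gain | ρ | Assessment effect | Program arm pre-post | Either of these | Condition effect | Interaction | Between-arm difference in change |
|---|---|---|---|---|---|---|---|
| 0 | 0.5 | 5.0% | 5.1% | 8.9% | 5.0% | 4.9% | 5.1% |
| 0 | 0.7 | 5.0% | 5.1% | 9.0% | 4.9% | 4.6% | 5.1% |
| 0.3 SD | 0.5 | 42.4% | 22.4% | 47.6% | 4.9% | 5.2% | 5.0% |
| 0.3 SD | 0.7 | 64.7% | 33.7% | 68.9% | 4.9% | 5.2% | 5.1% |
| 0.5 SD | 0.5 | 86.6% | 52.0% | 88.4% | 5.0% | 5.1% | 5.0% |
| 0.5 SD | 0.7 | 98.1% | 73.0% | 98.4% | 4.8% | 5.0% | 5.1% |

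The formulas and the simulation agree.

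**Step 5. Comparing significance across arms.** The arms are independent and have the same rejection rate p, so the program arm is significant and the control arm is not with probability p(1 − p). For s = 0.3 this is 0.224 × 0.776 = 17% (ρ = 0.5) and 0.337 × 0.663 = 22% (ρ = 0.7). For s = 0.5 it is 0.52 × 0.48 = 25% and 0.73 × 0.27 = 20%.

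**The case against.** The strongest case on the other side is about what the plan actually commits to.

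- **No rule exists.** A reader might infer that Aim 3 lays down a rule by which a significant assessment effect or within-group test establishes promise. It does not. It says promise will be examined through ANOVAs, and the post-hoc tests come in a separate sentence that does not mention promise. This stands.
- **The wording on assessment is ambiguous.** The phrase may simply identify the within-subject factor. The plural main effects favors reading it as a tested effect but does not settle the matter. This stands too, though the within-group tests are explicit on any reading.
- **Between-arm evidence is planned.** The condition main effect, the between-group post-hoc tests and, on its natural reading, Cohen's d on change all compare the arms. Standard ANOVA output would normally show the interaction as well. This limits the concern but does not remove it: none of these is given priority, the interaction is not named, and the text does not state that d is between arms.
- **The shared gain is assumed.** The documents give no control-arm change, and Control Condition says the usefulness of tip sheets alone is unknown. Shared change is easier to expect on knowledge items than on the 52-item problem-solving inventory. The rates are therefore conditional.
- **This is a pilot.** The protocol leaves longer-term assessment of efficacy to later, larger trials, and Table 4 contains no significance-based go/no-go step. That bears on how serious the point is. It does not make a within-arm test informative about the program.

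**Conclusion.** The concern holds as a gap in specification. Aim 3 names no deciding contrast, omits the interaction, and places tests that do not compare the arms beside tests that do. That the former cannot separate program benefit from shared change follows from their construction and needs no assumption.

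The size does rest on assumptions: alpha 0.05, correlation 0.5 to 0.7, normal data at three occasions, 18 per arm and a shared gain that is sustained. Under these, the assessment effect is significant in about 42-65% of trials at a shared 0.3 SD and 87-98% at 0.5 SD, against about 5% for the interaction. With no shared gain it also rejects at about 5%.

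Two stronger readings are not supported. The plan does not say that promise will be declared from these tests; it only fails to exclude it. Nor do the rates apply to every listed outcome: the plan of action is rated at Time 2, quality of life is measured at Times 1 and 3 only, and family communication is a single 3-point item.

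The sponsor should correct this before analysis. It does not affect the trial's conduct.

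**What to change.** In Data Analysis, Aim 3:
1. State that promise is judged on one named between-arm contrast, either the condition by assessment interaction or the baseline-adjusted difference between arms at follow-up, reported with its 95% CI.
2. State that Cohen's d is the between-arm difference in pre-to-post change.
3. Report the assessment effect and the within-arm changes, with CIs, as description only, and say that significance will not be compared across arms.

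The cost is a few sentences and no new data. The downside is fewer nominally significant results to report. The contrast will also be imprecise at this size: for a true gain in the program arm only, simulated interaction power is 31-48% at 0.5 SD and 68-89% at 0.8 SD (ρ 0.5 to 0.7). That is a reason to put the confidence interval first. The condition main effect would not be a better choice: because it averages in the baseline, its power is 19-22% and 41-48% in the same scenarios.
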